1. INTRODUCTION

This statistical analysis plan (SAP) describes the statistical analysis methods and data presentations to be used in tables, figures, and listings (TFLs) in the clinical study report (CSR) for Study GS-US-419-4015. This SAP is based on the study protocol Amendment 3 dated 04 February 2020 and the electronic case report form (eCRF). The SAP will be finalized before database finalization. Any changes made after the finalization of the SAP will be documented in the CSR.

1.1. Study Objectives

[figure not shown]
The primary objective of this study is:

- To evaluate the efficacy of filgotinib, when compared to placebo, in establishing clinical remission, defined as CDAI < 150, at Week 24

The secondary objectives of this study are:

- To evaluate the impact of filgotinib, when compared to placebo, on change in segmental MaRIA score for all assessed small bowel segments at Week 24
- To evaluate the efficacy of filgotinib, when compared to placebo, in establishing segment level MaRIA remission at Week 24
- To evaluate the efficacy of filgotinib, when compared to placebo, in establishing segment level MaRIA response at Week 24
- To evaluate the efficacy of filgotinib, when compared to placebo, in establishing subject level small bowel MaRIA remission at Week 24
- To evaluate the efficacy of filgotinib, when compared to placebo, in establishing subject level small bowel MaRIA response at Week 24
- To evaluate the efficacy of filgotinib, when compared to placebo, in establishing clinical remission, defined as CDAI < 150, at Week 10
- To evaluate the impact of filgotinib, when compared to placebo, on change in CDAI scores
- To evaluate the safety and tolerability of filgotinib

CCI

1.2. Study Design

[figure not shown]
This is a Phase 2 randomized, double-blind, placebo-controlled study to evaluate the efficacy and safety of filgotinib in treating subjects with SBCD. A schematic of this study is provided in [Figure 1-1](#). Subjects who meet protocol eligibility criteria will be randomized in a blinded fashion to 1 of 3 treatment groups in a 2:2:1 ratio:

- **Treatment group 1 (n = 40):** Filgotinib 200 mg and placebo-to-match (PTM) filgotinib 100 mg, once daily
- **Treatment group 2 (n = 40):** Filgotinib 100 mg and PTM filgotinib 200 mg, once daily
- **Treatment group 3 (n = 20):** PTM filgotinib 200 mg and PTM filgotinib 100 mg, once daily

Note: United States (US) males who have not failed at least 2 prior biologic therapies (ie, any tumor necrosis factor-alpha [TNF α] antagonist and vedolizumab) will be randomized in a 2:1 ratio to receive either filgotinib 100 mg or matching placebo.

Figure 1-1.

Study Design Schematic

FIL filgotinib; PBO placebo; mg milligram.

*Non responders are subjects who never achieved a ≥ 70 point CDAI reduction from baseline or CDAI < 150 at any point up to and including Week 10

**Disease worsening is defined as a ≥ 100 point increase in CDAI score from the Week 10 value and CDAI score ≥ 220 points at 2 consecutive visits

CCI

Treatment assignments will be stratified according to the following factors:

- Concomitant use of oral, systemically absorbed corticosteroids (eg, prednisone) at Day 1, (Yes or No)
- Concomitant use of immunomodulators (eg, 6-mercaptopurine [6-MP], azathioprine, methotrexate [MTX]) at Day 1, (Yes or No)
- Prior exposure to biologics (eg, TNF α antagonists or vedolizumab), (Yes or No)

This study includes:

- Screening (Days -30 to -1)
- Randomization (Day 1)

- Blinded treatment (Day 1 to Week 24)

Efficacy assessment: At Week 24, CDAI score to assess clinical remission; MRE to assess radiographic changes

cc1 [REDACTED]

cc1 [REDACTED]

- Post-Treatment (PTx) safety assessments

cc1 [REDACTED]

cc1 [REDACTED]

cc1 [REDACTED]

- Steroid tapering must begin at Week 10 for subjects who are considered responders.

1.3. Sample Size and Power

A sample size of 40 subjects in each of the filgotinib treatment groups and 20 subjects in the placebo group is considered adequate to assess the safety, tolerability, and efficacy of filgotinib in a descriptive manner. Assuming a clinical remission rate of 40% for the filgotinib treatment groups (200 mg and 100 mg), the 2-sided 90% exact confidence interval is (26.9%, 54.2%). The clinical remission rate for placebo group is assumed to be 20%.

2. TYPE OF PLANNED ANALYSIS

2.1. Data Monitoring Committee (DMC) Analyses

An external multidisciplinary DMC will review the progress of the study and perform interim reviews of the safety data in order to protect subject welfare and preserve study integrity. The DMC is to recommend to the sponsor whether the nature, frequency, and severity of adverse effects associated with the study treatment warrant the early termination of the study in the best interests of the participants, whether the study should continue as planned, or the study should continue with modifications.

The DMC will meet twice to evaluate all available safety data from the study. The initial meeting will occur after approximately 20% of the planned total number of subjects reach the Week 10 visit. Following this, the next meeting will occur after approximately 50% of the subjects reach the Week 10 visit. Additional DMC meetings may be convened, if needed.

The DMC's role and responsibilities and the scope of analysis to be provided to the DMC are described in a mutually agreed upon charter, which defines the DMC membership, meeting logistics, and meeting frequency.

No formal interim efficacy analysis, which may lead to early termination for efficacy or futility, is planned.

2.2. Final Analysis

After all enrolled subjects have completed the study, outstanding data queries have been resolved or adjudicated as unresolvable, and the data have been cleaned and finalized, the study blind will be broken and the final analysis of the data will be performed.

3. GENERAL CONSIDERATIONS FOR DATA ANALYSES

Analysis results will be presented using descriptive statistics. For categorical variables, the number and percentage of subjects in each category will be presented; for continuous variables, the number of subjects (n), mean, standard deviation (SD) or standard error (SE), median, first quartile (Q1), third quartile (Q3), minimum, and maximum will be presented. By-subject listings will be presented for all subjects in the All Randomized Analysis Set and sorted by subject ID number, visit date, and time (if applicable). Data collected on log forms, such as AEs, will be presented in chronological order within subject. The treatment group to which subjects were randomized will be used in the listings. Age, sex at birth, race, and ethnicity will be included in the listings, as space permits.

3.1. Analysis Sets

Analysis sets define the subjects to be included in an analysis. Analysis sets and their definitions are provided in this section. The analysis set will be identified and included as a subtitle of each table, figure, and listing.

For each analysis set, the number and percentage of subjects eligible for inclusion, as well as the number and percentage of subjects who were excluded and the reasons for their exclusion, will be summarized by treatment group.

A listing of reasons for exclusion from analysis sets will be provided by subject.

3.1.1. All Randomized Analysis Set

All Randomized Analysis Set includes all subjects who were randomized in the study.

The All Randomized Analysis Sets are the primary analysis sets for by-subject listings.

3.1.2. Full Analysis Set

The Full Analysis Set (FAS) includes all randomized subjects who took at least 1 dose of study drug. This is the primary analysis set for efficacy analyses.

3.1.3. Safety Analysis Set

The Safety Analysis Set includes all subjects who took at least 1 dose of study drug. This is the primary analysis set for safety analyses.

CCI

[REDACTED]

CCI

3.2. Subject Grouping

For analyses based on the All Randomized Analysis Set and FAS, subjects will be grouped according to the treatment to which they were randomized. For analyses based on the Safety Analysis Set CCI [REDACTED], subjects will be grouped according to the actual treatment received. The actual treatment received will differ from the randomized treatment only when their actual treatment differs from randomized treatment for the entire treatment duration.

CCI

3.3. Strata and Covariates

Subjects will be randomly assigned to treatment groups via the interactive web response system (IWRS) in a 2:2:1 ratio using a stratified randomization schedule. Stratification will be based on the following variables:

- Concomitant use of oral, systemically absorbed corticosteroids (eg, prednisone) at Day 1, (Yes or No)
- Concomitant use of immunomodulators (eg, 6-MP, azathioprine, methotrexate) at Day 1, (Yes or No)
- Prior exposure to biologics (eg, TNF α antagonists or vedolizumab), (Yes or No)

If there are discrepancies in stratification factor values between the IWRS and the clinical database (eCRF data), the values recorded in the clinical database will be used for analyses. For derivation of concomitant medication use at Day 1, the start date of such medication should be before or on the same date of the first dose of study drug and with either the stop date of such medication being on or after the first dose of study drug or with “ongoing” status.

Efficacy endpoints will be evaluated using stratification factors as covariates or stratification variables for analyses, as specified in Section 6.

3.4. Examination of Subject Subgroups

There are no prespecified subject subgroupings for efficacy and safety analyses.

3.5. Missing Data and Outliers

3.5.1. Missing Data

In general, missing data will not be imputed unless methods for handling missing data are specified. Exceptions are presented in this document.

For missing last dosing date of study drug, imputation rules are described in Section 4.2.1. Imputation and calculation rules for missing patient diary data and other CDAI components are described in [Appendix 3](#). Imputation and calculation rules for missing MaRIA data are described in Section 6.3. The handling of missing or incomplete dates for AE onset is described in Section 7.1.5.2, and for prior and concomitant medications in Section 7.4.

Values for missing safety laboratory data will not be imputed. However, a missing baseline result will be replaced with a screening result, if available. If no pre-treatment laboratory value is available, the baseline value will be assumed to be normal (ie, no grade) for the summary of graded laboratory abnormalities. If safety laboratory results for a subject are missing for any reason at a time point, the subject will be excluded from the calculation of summary statistics for that time point.

Values for missing vital signs data will not be imputed. However, a missing baseline result will be replaced with a screening result, if available.

3.5.2. Outliers

Outliers will be identified during the data management and data analysis process. All data, including outliers, will be included in the data analysis, unless otherwise specified.

3.6. Data Handling Conventions and Transformations

In general, age (in years) on the date of the first dose of study drug will be used for analyses and presentation in listings. If an enrolled subject was not dosed with any study drug, the randomization date will be used instead of the first dosing date of study drug. For screen failures, the date the informed consent was signed will be used for age calculation. If only the birth year is collected on the eCRF, “01 July” will be used for the unknown birth day and month for the purpose of age calculation. If only birth year and month are collected, “15” will be used for the unknown birth day.

Duration of CD (years) is the number of years between the diagnosis date of CD and date of first dose of study drug. The partial diagnosis date of CD (if any) will be imputed for calculation as follows:

- If day and month are missing but year is available, then the imputed day and month will be 01 Jan.
- If day is missing but the month and year are available, then the imputed day will be the first day of the month.
- Partial date will not be imputed if the year is missing.

Non-PK data that are continuous in nature but are less than the lower limit of quantitation (LOQ) or above the upper LOQ will be imputed as follows:

- A value that is 1 unit less than the LOQ will be used for calculation of descriptive statistics if the datum is reported in the form of “ $< x$ ” (where x is considered the LOQ). For example, if the values are reported as < 50 and < 5.0 , values of 49 and 4.9, respectively, will be used for calculation of summary statistics. An exception to this rule is any value reported as < 1 or < 0.1 , etc. For values reported as < 1 or < 0.1 , a value of 0.9 or 0.09, respectively, will be used to calculate summary statistics.
- A value that is 1 unit above the LOQ will be used for calculation of descriptive statistics if the datum is reported in the form of “ $> x$ ” (where x is considered the LOQ). Values with decimal points will follow the same logic as above.
- The LOQ will be used for calculation of descriptive statistics if the datum is reported in the form of “ $\leq x$ ” or “ $\geq x$ ” (where x is considered the LOQ).

Natural logarithm transformation will be used for plasma concentrations. Plasma concentration values that are below the limit of quantitation (BLQ) will be presented as “BLQ” in the concentration data listing. Values that are BLQ will be treated as 0 at predose time points, and one-half the value of the LOQ at postbaseline time points.

The following conventions will be used for the presentation of summary and order statistics:

- If at least 1 subject has a concentration value of BLQ for the time point, the minimum value will be displayed as “BLQ.”
- If more than 25% of the subjects have a concentration data value of BLQ for a given time point, the minimum and Q1 values will be displayed as “BLQ.”
- If more than 50% of the subjects have a concentration data value of BLQ for a given time point, the minimum, Q1, and median values will be displayed as “BLQ.”
- If more than 75% of the subjects have a concentration data value of BLQ for a given time point, the minimum, Q1, median, and Q3 values will be displayed as “BLQ.”
- If all subjects have concentration data values of BLQ for a given time point, all order statistics (minimum, Q1, median, Q3, and maximum) will be displayed as “BLQ.”

3.7. Analysis Visit Windows

3.7.1. Definitions

The First Dosing Date is defined as the date when subjects take the first dose of study drug, as recorded in the Study Drug Administration eCRF.

The Last Dosing Date is defined as the date when subjects take the last dose of study drug as recorded in the Study Drug Administration eCRF.

Study Day will be calculated from the first dosing date of study drug and derived as follows:

- For days on or after first dosing date: Assessment Date = First Dosing Date + 1
- For days prior to the first dosing date: Assessment Date = First Dosing Date

Therefore, Study Day 1 is the day of the first dose of study drug administration.

Baseline is defined as the last available observation on or prior to the first dosing date, unless specified otherwise.

3.7.2. Analysis Visit Windows

Subject visits may not occur on protocol-specified days. Therefore, for the purpose of analysis, observations will be assigned to analysis windows.

The analysis windows for efficacy endpoints including CDAI, PRO2, **CCI** endpoints are based on study day and are provided in [Table 3-1](#).

The analysis windows for MaRIA score-related efficacy endpoints are based on study day and provided in [Table 3-2](#).

The analysis windows for body weight, vital signs, ECG, safety laboratory parameters (hematology, chemistry, fasting lipid profile, and serum immunoglobulin), **CCI** are provided in

[Table 3-3](#).

Table 3-1 Analysis Visit Windows for CDAI, PRO2 CCI -related Endpoints

Nominal Visit	Analysis Visit	Nominal Day (Study Day)	Lower Limit (Study Day)	Upper Limit (Study Day)
Screening/Day 1	Baseline	1	(none)	1
Week 2	Week 2	15	2	22
Week 4	Week 4	29	23	36
Week 6	Week 6	43	37	57
Week 10	Week 10	71	58	85
Week 14	Week 14	99	86	113
Week 18	Week 18	127	114	141
Week 24	Week 24	169	142	197

Note: For analysis purpose, PRO2 from Screening and Visit Day 1 will be calculated and both visits will be considered for the derivation of baseline, which is defined as the last available observation on or prior to the first dosing date of the study drug.

CCI

Table 3-2 Analysis Visit Windows for MaRIA Score-related Efficacy Endpoints

Nominal Visit	Analysis Visit	Nominal Day (Study Day)	Lower Limit (Study Day)	Upper Limit (Study Day)
Screening	Baseline	1	(none)	1
Week 24	Week 24	169	142	197

Table 3-3 Analysis Visit Windows for Body Weight, Vital Signs, ECG, Hematology, Chemistry, Fasting Lipid Profile, Serum Immunoglobulin, CCI CCI

Nominal Visit	Analysis Visit	Nominal Day (Study Day)	Lower Limit (Study Day)	Upper Limit (Study Day)
Screening/Day 1	Baseline	1	(none)	1
Week 2	Week 2	15	2	22
Week 4	Week 4	29	23	36
Week 6	Week 6	43	37	57
Week 10	Week 10	71	58	85
Week 14	Week 14	99	86	113
Week 18	Week 18	127	114	141
Week 24	Week 24	169	142	≥ 169

Note: ECG is collected postbaseline at Week 10 and the corresponding analysis windows will be applied; fasting lipid profile, CCI are collected postbaseline at Weeks 10 and 24 and the corresponding analysis windows will be applied; serum immunoglobulin is collected postbaseline at Weeks 4, 10, and 24 and the corresponding analysis windows will be applied.

An unscheduled visit prior to the first dosing of study drug may be included in the calculation of the baseline value, if applicable.

3.7.3. Selection of Data in the Event of Multiple Records in an Analysis Visit Window

Depending on the statistical analysis method, single values may be required for each analysis window. For example, change from baseline by visit usually requires a single value, whereas a time-to-event analysis would not require 1 value per analysis window.

If multiple, valid, nonmissing, continuous measurements exist in an analysis window, records will be chosen based on the following rules if a single value is needed:

- In general, the baseline value will be the last nonmissing value on or prior to the first dosing date of study drug, unless otherwise specified. If multiple measurements occur on the same day, the last nonmissing value prior to the first dosing date of study drug will be considered as the baseline value. If these multiple measurements occur at the same time or the time is not available, the average of these measurements (for continuous data) will be considered the baseline value.
- For postbaseline visits:

The record closest to the nominal day for that visit will be selected.

If there are 2 records that are equidistant from the nominal day, the later record will be selected.

If there is more than 1 record on the selected day, the average will be taken, unless otherwise specified.

If multiple, valid, nonmissing, categorical measurements exist in an analysis window, records will be chosen based on the following rules if a single value is needed:

- For baseline, the last available record on or prior to the date of the first dose of study drug will be selected. If there are multiple records with the same time or no time recorded on the same day, the value with the lowest severity will be selected (eg, normal will be selected over abnormal for safety ECG findings).
- For postbaseline visits:

The record closest to the nominal day for that visit will be selected.

If there are 2 records that are equidistant from the nominal day, the later record will be selected.

If there is more than 1 record on the selected day, the worst severity will be taken (eg, abnormal will be selected over normal for safety ECG findings), unless otherwise specified.

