### **3.5.2. Study Drug Discontinuation Considerations**

The Gilead Medical Monitor should be consulted prior to study drug discontinuation when medically feasible.

Study drug must be permanently discontinued in the following instances:

- Any opportunistic infection
- Any **serious** infection that requires antimicrobial therapy or hospitalization, or any infection that meets SAE reporting criteria.
- Febrile neutropenia (temperature  $> 38.3^{\circ}\text{C}$  or a sustained temperature of  $> 38^{\circ}\text{C}$  for more than one hour) with absolute neutrophil count of  $< 1,000/\text{mm}^3$
- Symptomatic anemia (eg, signs/symptoms including pallor, shortness of breath, new heart murmur, palpitations, lethargy, fatigue) with hemoglobin  $< 7.5\text{ g/dL}$ , or if transfusion is indicated regardless of hemoglobin value
- Complicated herpes zoster infection (with multi-dermatomal, disseminated, ophthalmic, or CNS involvement)
- Evidence of active Hepatitis C Virus (HCV) during the study, as evidenced by HCV RNA positivity
- Evidence of active Hepatitis B Virus (HBV) during the study, as evidenced by HBV DNA positivity
- Any thromboembolic event that meets SAE reporting criteria
- Unacceptable toxicity, or toxicity that, in the judgment of the investigator, compromises the subject's ability to continue study-specific procedures or is considered to not be in the subject's best interest
- Subject request to discontinue for any reason
- Subject noncompliance
- Pregnancy during the study; refer to Section [7.7.2.1](#)
- Discontinuation of the study at the request of Gilead, a regulatory agency or an institutional review board or independent ethics committee (IRB/IEC)
- Subject use of prohibited concurrent therapy *may* trigger study drug discontinuation; consultation should be made with the Gilead Medical Monitor.

- **Laboratory Criteria:** After becoming aware of any of the below described abnormal laboratory changes occurring at any one time, an unscheduled visit (ie, sequential visit) should occur to retest within 3 to 7 days (except creatinine, which should be retested 7 to 14 days apart).

Two sequential neutrophil counts < 750 neutrophils/mm^3 (SI: < 0.75 x10^9 cells/L)

Two sequential (3 to 5 days apart) platelet counts  
< 75,000 platelets/mm^3 (SI: < 75.0 x10^9 cells/L)

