2 sequential aspartate aminotransferase (AST) or alanine aminotransferase (ALT) elevations > 3x the upper limit of normal (ULN) and at least one of the following confirmed values:

- total bilirubin >2x ULN
- INR > 1.5
- or accompanied by symptoms consistent with hepatic injury

For any subject with an **initial** AST or ALT elevation > 3x the ULN, at the time of the **second confirmatory draw**, an INR, prothrombin time (PT) and partial thromboplastin time (PTT) must also be drawn

Two sequential AST or ALT > 5 x ULN

Two sequential values for estimated creatinine clearance (CLcr) < 35 mL/min based on the Cockcroft-Gault (CC&G) formula

$$\text{Male: } \frac{(140 - \text{age in years}) \times (\text{wt in kg})}{72 \times (\text{serum creatinine in mg/dL})} \text{ CL}_{\text{cr}} \text{ (mL/min)}$$

$$\text{Female: } \frac{(140 - \text{age in years}) \times (\text{wt in kg}) \times 0.85}{72 \times (\text{serum creatinine in mg/dL})} \text{ CL}_{\text{cr}} \text{ (mL/min)}$$

Subjects are free to withdraw from the study at any time without providing reason(s) for withdrawal and without prejudice to further treatment. The reason(s) for withdrawal will be documented in the electronic case report form (eCRF).

Subjects who permanently discontinue study drug for any reason should discuss their continued care plan with their physician.

Subjects who permanently discontinue study drug for pregnancy should not continue in the study; if there are any questions regarding permanent discontinuation, these should be discussed with the Sponsor.

Subjects withdrawing from the study should complete Early Termination (ET), followed by PTx assessments 30 days after the last dose of study drug.

Reasonable efforts will be made to contact subjects who are lost to follow-up. All contacts and contact attempts must be documented in the subject's file.

The Sponsor has the right to terminate the study at any time in case of safety concerns or if special circumstances concerning the study medication or the company itself occur, making further treatment of subjects impossible. In this event, the investigator(s) and relevant authorities will be informed of the reason for study termination.

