7. SAFETY ANALYSES

Unless otherwise specified, summaries of safety data will be provided for the Safety Analysis Set and will include data collected up to the last dose of study drug plus 30 days.

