Appendix 1. Schedule of Assessments

Period	Screening	Treatment										Follow-Up	
		1	2	3	4	5	6	7	8	9	10	PTx ^a	ET
Visit	1	0	2	4	6	10	14	18	20	24			
Week													
Study Day	-30 to -1	1	15	29	43	71	99	127	141	169			
Visit Window (±)			±3	±3	±3	±2	±3	±3	±5	±5		±3	
Written Informed Consent	X												
Medical History & Demographics	X												
Crohn's Disease & Treatment History	X												
12 lead ECG	X						X						X ^b
Review of Inclusion/Exclusion Criteria	X	X											
Complete Physical Examination ^c	X												
Symptom Directed Physical Examination ^c		X	X	X	X	X	X	X			X	X	X
Vital Signs	X	X	X	X	X	X	X	X			X	X	X
Weight	X	X	X	X	X	X	X	X			X	X	X
Height	X												
Adverse Events	X	X	X	X	X	X	X	X			X	X	X
Concomitant Medications	X	X	X	X	X	X	X	X			X	X	X
Randomization		X											
Study Drug Dispensing		X		X		X	X	X					
CDAI ^d	X		X	X	X	X	X	X			X		X
PRO2 ^d	X		X	X	X	X	X	X			X		X
eDiary instruction & review ^e	X	X	X	X	X	X	X	X			X		
MRE with segmental & global MaRIA scores ^o	X										X		
Stool for C. diff toxin, pathogenic E. coli , Salmonella , Shigella ,	X												

Period	Screening	Treatment										Follow-Up	
		1	2	3	4	5	6	7	8	9	10	PTx ^a	ET
Visit	1	2	3	4	5	6	7	8	9	10			
Week		0	2	4	6	10	14	18	20	24			
Study Day	-30 to -1	1	15	29	43	71	99	127	141	169			
Visit Window (±)			±3	±3	±3	±2	±3	±3	±5	±5	±3		
Campylobacter and Yersinia testing													
Stool O&P	X												
CCI													
Fecal MMP 9	X										X		
CCI													
Urine drug screen ^f	X												
Urinalysis ^g	X											X	
Pregnancy test ^g	X	X		X	X	X	X	X	X	X	X	X	X
TB screening ^h	X												
Chest x ray ^g	X												
HBV, HCV, HIV screening ⁱ	X												
Hematology	X	X	X	X	X	X	X	X			X	X	X
Chemistry	X	X	X	X	X	X	X	X			X	X	X
Fasting Lipids ^j		X				X					X		
CCI													
Blood transcriptome sample		X		X		X					X		
vfPBMC ^k		X		X		X					X		
Serum immunoglobulin		X		X		X					X	X	X
CCI													
CCI													

- a The Post Treatment (PTx) visit should occur 30 days after the last dose of study drug. **CCI**
- b For subjects who terminate prior to Week 10
- c A complete physical examination (PE) including, vital signs, body weight, and height will be performed at screening. A symptom directed PE may be done at other time points.
- d The screening CDAI will be used as the Day 1 measurement. The CDAI patient reported outcomes of stool frequency and abdominal pain will be used to derive the PRO2 score.

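### SAP Table 3-3 assigns safety records by study day alone, so post-treatment values of subjects who stop study drug early can be summarized as Week 4 to Week 24 values

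*SAP*

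**What the plan says.** **Windows.** In SAP 3.7.2 the sentence that sends safety data to Table 3-3 begins "The analysis windows for body weight, vital signs, ECG, safety laboratory parameters (hematology, chemistry, fasting lipid profile, and serum immunoglobulin". The table runs from Baseline to Week 24 and sorts by study day only. Its last row has nominal day 169, lower limit 142 and upper limit ≥ 169; Tables 3-1 and 3-2 give 197 in that cell. No row follows Week 24, and nothing in the section refers to the last dosing date. The table note limits one analyte: "serum immunoglobulin is collected postbaseline at Weeks 4, 10, and 24 and the corresponding analysis windows will be applied".

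**Selection within a window.** For postbaseline visits SAP 3.7.3 says "The record closest to the nominal day for that visit will be selected", and for ties "If there are 2 records that are equidistant from the nominal day, the later record will be selected".

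**Data cut.** Under SAP 7, safety summaries "will include data collected up to the last dose of study drug plus 30 days". SAP 7.2 repeats this for laboratory data.

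**Post-treatment visit.** SAP Appendix 1, footnote a: "The Post Treatment (PTx) visit should occur 30 days after the last dose of study drug". The schedule gives it a window of ±3 days and marks weight, vital signs, hematology, chemistry and serum immunoglobulin there, but not ECG or fasting lipids.

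**Early stopping.** Protocol 3.5.2 opens a list with "Study drug must be permanently discontinued in the following instances". The list includes infections and confirmed neutrophil, platelet, liver-enzyme and creatinine-clearance criteria. It adds: "Subjects withdrawing from the study should complete Early Termination (ET), followed by PTx assessments 30 days after the last dose of study drug".

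**Outputs.** SAP 7.2.1 and 7.3 summarize values and changes at each postbaseline time point, and 7.2.1 plots selected laboratory tests by analysis visit. Protocol 8.6.3 promises laboratory summaries at all scheduled time points.

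**The concern.** A reader of a by-visit safety table will take the Week 18 row as describing subjects about 18 weeks into treatment. Under the rules as written, that row can also hold values from subjects who have been off drug for about a month. Nothing in the table would mark them.

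The clearest case is a subject stopped under the laboratory criteria of Protocol 3.5.2. The off-drug value of the very parameter that led to the stop can appear in a later week's row. If it has recovered, the row looks better than treatment warrants. If it has not, the reader still cannot tell that it is off-drug.

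Inclusion is also arbitrary. A post-treatment visit at +27 to +30 days enters the tables, while one at +31 to +33 days, still inside its ±3-day window, is dropped by the cut.

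**Working it through.** **Inputs.** Windows from Table 3-3: Week 4, 23–36; Week 6, 37–57; Week 10, 58–85; Week 14, 86–113; Week 18, 114–141; Week 24, from 142. Selection rule from SAP 3.7.3. Visit at last dose L + 30 days, window ±3. Data kept to L + 30.

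**The table's own limits.** Midpoints between nominal days reproduce the upper limits 22, 36, 57, 85 and 113, for example (43 + 71)/2 = 57. The Week 18 limit is 127 + 14 = 141, and the 197 in Tables 3-1 and 3-2 is 169 + 28. No such rule gives ≥ 169.

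**Step 1: which row a visit at L + 30 falls in.**

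| Last dose (Day) | Post-treatment visit (Day) | Row |
|---|---|---|
| 1–6 | 31–36 | Week 4 |
| 7–27 | 37–57 | Week 6 |
| 28–55 | 58–85 | Week 10 |
| 56–83 | 86–113 | Week 14 |
| 84–111 | 114–141 | Week 18 |
| 112 or later | 142 or later | Week 24 |

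With the visit at +27, each boundary moves up 3 days. For stops at scheduled visits: last dose Day 43 gives Day 73 (Week 10 row, 2 days from nominal), Day 99 gives Day 129 (Week 18 row, 2 days), and Day 127 gives Day 157 (Week 24 row, 12 days). Immunoglobulin is exposed only in the Week 4, 10 and 24 rows.

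**Step 2: competition with a record taken on the last dosing day, L up to 141.** The Week 4 to Week 18 rows are 14 to 28 days wide, so records at L and L + 30 never share a row. At +27 they share one only for L = 58, 86 or 114. There the on-drug record is closer (for L = 58, 71 − 58 = 13 days against 85 − 71 = 14) and is kept.

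**Step 3: the same competition inside the Week 24 row, L from 142.** The post-treatment value is selected if L + 30 − 169 ≤ 169 − L, that is 2L ≤ 308, so L ≤ 154. At L = 154 the distances tie at 15 days and the later record wins. Example: last dose and sample on Day 150 (19 days from 169), post-treatment sample on Day 180 (11 days). Day 180 is reported as Week 24. At L = 155 it is 16 against 14 days, and the on-drug record is kept.

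**Step 4: completers.** Assume the last dose is at the Week 24 visit, Day 164–174. That visit is at most 5 days from nominal. The post-treatment visit falls on Day 191–207 (at most 174 + 30 = 204 after the cut), so at least 191 − 169 = 22 days from nominal. It is selected in 0 of 77 combinations of visit day and offset. It enters only if the Week 24 value is missing or excluded (hemolyzed sample, local-laboratory hematocrit, home-measured weight).

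**Step 5: would a real upper limit be enough?** The rules were run for every last-dose day from 1 to 169, with visits on nominal days, a sample on the last dosing day and the post-treatment visit at +30.

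| Rule | Last-dose days for which the post-treatment value is reported in a week row |
|---|---|
| Table 3-3 as written | 154 of 169 |
| Week 24 capped at Day 197 | 154 of 169 |
| Week 24 capped at Day 174 | 144 of 169 |
| Post-treatment records assigned first, by last dosing date | 0 of 169 |

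These are counts of possible last-dose days, not of subjects.

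**The case against.** **The inclusion is deliberate.** Protocol 8.6 requires safety data to 30 days after discontinuation to be summarized, and the SAP speaks of analysis visits and postbaseline time points without calling them on-treatment. This stands as a reason to keep the data. It does not justify labeling a post-treatment visit Week 18, and Protocol 8.6.3 points to giving that scheduled visit its own place.

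**Other samples may be chosen instead.** An early-termination sample, or a retest under Protocol 3.5.2 (3 to 7 days; 7 to 14 for creatinine), may fall in the same row closer to nominal. This stands. With last dose Day 110, a retest on Day 117 is 10 days from Day 127, the post-treatment visit on Day 140 is 13, and the retest is selected. It does not remove the problem. For last doses on Days 43, 71, 99 and 127, a retest 14 days later falls on Days 57, 85, 113 and 141, each still in the earlier row.

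**The signal is visible elsewhere.** Treatment-emergent, marked and liver abnormality summaries do not use these windows, and the listings are chronological. The line plots show medians and quartiles, which one value barely moves. This stands, and it limits the point to the by-visit summaries.

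**The count is unknown.** This also stands. A reader might infer from Protocol 3.4 that all Week 10 non-responders supply off-drug values to the Week 14 row (Day 71 + 30 = Day 101). The documents do not support that. Text on what follows non-response and on the post-treatment visit is redacted, and Protocol 1.5 mentions early access to active drug after Week 10.

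**Conclusion.** The point holds for subjects who stop study drug early. Following the SAP as written can put a value taken 27 to 30 days after the last dose into a Week 4 to Week 24 row. For a visit at +30 this happens for last doses through Day 154, assuming an on-drug sample on the last dosing day and no closer sample afterwards. One such value is 1/40 = 2.5% of a full filgotinib row or 1/20 = 5% of the placebo row, and more where other values are missing. The number of subjects cannot be stated and may be small. It is a minor correction to descriptive safety tables.

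Three stronger readings are tempting and fail:

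- That post-treatment values generally replace Week 24. The closest-record rule protects completers who have a usable Week 24 value.
- That the ≥ 169 entry is the cause. It is an error, but a cap at 197 changes nothing in Step 5. The cause is assignment by study day without reference to the last dose.
- That every early stopper adds such a value. Last doses on Days 155–163 with a last-day record do not (visit at +30), nor do Days 58, 86 and 114 at +27, nor immunoglobulin falling in the Week 6, 14 or 18 rows.

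No efficacy endpoint uses Table 3-3.

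**What to change.** In SAP 3.7.2, before the study-day windows are applied, assign post-treatment visit records to their own post-treatment analysis visit, keyed to the last dosing date, and summarize them there. This fits Protocol 8.6 and 8.6.3. Flagging the records and leaving them out altogether would not, because a scheduled time point would then be missing from the by-visit summaries.

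Replace ≥ 169 in the Week 24 row with a real upper limit. The value 197 would match Tables 3-1 and 3-2 but is not enough alone. Completers' post-treatment visits on Days 191–197, and visits at +30 after a last dose up to Day 167, would still fall inside the window.

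Keep the +30-day rule for treatment-emergent abnormalities.

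The cost is SAP wording and programming on data already collected. The downside is slightly fewer values in the later week rows and one extra row per table.
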